12.2 Package Insert/Summary of Product Characteristics

The appropriate package insert or Summary of Product Characteristics will be supplied to investigators in countries where the product is marketed.

12.3 Glossary of Abbreviations

Term/Abbreviation	Definition
ANCOVA	analysis of covariance
BAD	Barry-Albright Dystonia scale
BoNT-A	botulinum neurotoxin type A
BOTOX®	botulinum toxin type A purified neurotoxin complex (US Adopted Name, onabotulinumtoxinA)
CFR	Code of Federal Regulations (US)
CGI	Clinical Global Impression of Overall Change
CNS	central nervous system
C-SSRS	Columbia-Suicide Severity Rating Scale
ECG	electrocardiogram
eCRF	electronic case report form
EDC	electronic data capture
EMG	electromyography
EU	European Union
FDA	Food and Drug Administration
GAS	Global Attainment Scale
GCP	Good Clinical Practices
GMFCS-E&R	Gross Motor Function Classification System Expanded and Revised
HAT	Hypertonia Assessment Tool
HbA1c	glycosylated hemoglobin
HIPAA	Health Insurance Portability and Accountability Act Standards for Privacy of Individually Identifiable Health Information
ICH	International Conference on Harmonisation
IDR	Independent Drug Reconstitutor
IEC	Independent Ethics Committee
IRB	Institutional Review Board
IVRS	interactive voice response system
IWRS	interactive web response system
LS	least square
MACS	Manual Ability Classification System
MAS-B	Modified Ashworth Scale – Bohannon
Max	maximum

BOTOX® (Botulinum Toxin Type A) Purified Neurotoxin Complex

MI	multiple imputation
MMRM	Mixed Model Repeated Measures
mITT	modified intent-to-treat
MTS	Modified Tardieu Scale
NA	not applicable
No.	number
NOAEL	no-observable-adverse-effect level
OT	occupational therapy
PASS	power analysis and sample size
PT	physical therapy
██████████	██████████
R1	fast range of motion (R1 angle is the “angle of catch” after a fast velocity [V3] stretch)
R2	slow range of motion (R2 angle is the passive joint range of movement following a slow velocity [V1] stretch)
SDRC	Safety Data Review Committee
U	unit, corresponding to the median lethal dose (LD_{50}) in mice
US	United States
V1	slow velocity
V3	fast velocity

12.4 Protocol Amendment 1 Summary

Title: BOTOX® Treatment in Pediatric Upper Limb Spasticity: Double-blind Study

Protocol 191622-101, Amendment 1

Date of Amendment: 30 March 2012

Amendment Summary

This summary includes changes made to Protocol 191622-101 (02 December 2011) to provide clarifications, updated information, and corrections.

Following is a summary of content-oriented changes that were made to each section of the protocol, and a brief rationale for these changes. Minor editorial and document formatting revisions have not been summarized.

Section(s)	Revision	Rationale
Title page	Added EudraCT number and changed Allergan Medical Safety Physician.	Updated information.
4.4, Exclusion Criteria	Deleted number 12 and renumbered remaining criteria accordingly.	Number 12 duplicated 11b.
5.6.1, Treatment Regimen	In second paragraph, corrected 150 U to 100 U in “...maximum doses of 3 U/kg (not to exceed 100 U)...”	Corrected typographical error.
7.3.1, Primary Efficacy Analyses	Added wording to specify that if a pairwise comparison in MAS-B is not statistically significant, the corresponding pairwise comparison in CGI will not be considered statistically significant regardless of the actual p value.	Additional details added for clarification.
7.7, Additional Analysis/Inference for US FDA	Section 7.7 added to the protocol to clarify when dose effectiveness will be concluded.	Clarification added to address comments by US FDA during Special Protocol Assessment review.

Section(s)	Revision	Rationale
Table 1 (schedule), Footnote “i”; 8.3, Visits and Associated Procedures; and 12.1.16, CGI by Physician	Revised to clarify the ideal order of CGI and spasticity assessments.	Emphasis on these points was increased to reduce potential bias in CGI and spasticity assessments.
10.7, Handling of Biological Specimens	Revised approximate volume of blood collection for hematology and chemistry from 5 to 7 mL	Based on the revised central laboratory (Covance) requirements.
12.1.4, Hematology and Serum Chemistry	Revised reference ranges for alkaline phosphatase in Table 4.	Corrected values based on revised reference ranges provided by central laboratory (Covance).
12.1.17, Patient-reported Onset of Spasticity Symptom Relief	Revised the question from “have you noticed any treatment effect...” to “have you noticed any effect...”	Revised based on central IRB requirement to minimize potential bias in response.

12.5 Protocol Amendment 2 Summary

Title: BOTOX® Treatment in Pediatric Upper Limb Spasticity: Double-blind Study

Protocol 191622-101, Amendment 2

Date of Amendment: January 2014

Amendment Summary

This summary includes changes made to Protocol 191622-101 Amendment 1 (e-signature date 02 April 2012). This protocol was amended primarily to add assessment of suicidal ideation and behavior using the C-SSRS as a standard safety measure required by the US FDA's Division of Neurology Products for all ongoing or planned clinical studies, and to incorporate changes in statistical procedures.

Following is a summary of content-oriented changes that were made to each section of the protocol, and a brief rationale for these changes. Minor editorial and document formatting revisions have not been summarized.

Section(s)	Revision	Rationale
Title page	Referred to the Study Contacts Page for emergency telephone numbers; updated page 2	Per new Allergan protocol template
Protocol Summary	Amended Visit Schedule description to state there will be “approximately” 13 weekly OT sessions	Clarification
Protocol Summary; 2.2	Added distinction between US FDA and non US FDA clinical hypotheses and analyses	Clarification
Protocol Summary; Table 1; 6.2; 6.5; 7.3.4; 8.3.1; 8.3.3; 8.3.4; 8.3.5; 11; 12.1.18; 12.3	Specified that the C-SSRS is to be performed as a safety measure for patients \geq 6 years of age at day 1, and provided description of scale, data handling, and reference information	As requested by US FDA's Division of Neurology Products
Protocol Summary; Table 1; 6.1.3; 7.2.3; 7.3.3; 8.3.4; 8.3.5; 12.1.17	Added patient-reported benefit of injection	To collect patient-reported data on benefit of injection

Section(s)	Revision	Rationale
Protocol Summary; 4.4	Modified Exclusion Criterion 11a regarding seizure frequency for exclusion Modified Exclusion Criterion 12 regarding vulnerable respiratory state Added Exclusion Criterion 29 to exclude patients with significant risk of suicide from treatment Table 1 Added “Review safety lab results” to visit 3 Added “Access IVRS/IWRS” and clarified in new footnote (k) how and when IVRS/IWRS is used	Clarification Clarification To avoid confounding the safety data In agreement with Section 8.3.3 Clarification
3.1	Changed “members” to “participants” and removed “or investigator” from the examples given of ad hoc SDRC participants	Clarification
4.5.2	Added the statement that patients may stay in the study even if a prohibited medication is administered	Clarification
4.5.3	Moved and amended sentence regarding school-based therapy	Clarification that school-based therapy, if relevant per local legislation, is permitted during the study
5.3	Amended first paragraph regarding IDR	To clarify responsibilities of the IDR
5.5	Inserted sentence in first paragraph regarding IVRS/IWRS	To clarify that the site will access the system on day 1
Protocol Summary; 5.6.1; 8.3; 8.3.1	Amended to “approximately” 1-hour OT sessions	Clarification
5.6.1	Amended the first paragraph regarding patient’s weight and dose calculation	To clarify that patient’s weight in kilograms will be rounded to the nearest kilogram for dose calculation only
6.1.1; 6.1.2; 7.2; 7.2.1; 7.2.2	Made the distinction between US FDA measures and non-US FDA measures	Clarification
6.4	Corrected second bullet by removing “freezer” from the equipment needing temperature monitoring Added bullet that Allergan will supply a kilogram-only weight scale for selected sites, and that the site will supply it only if it is not already supplied by Allergan	Correction To ensure that patient’s weight is collected in kilograms only

Section(s)	Revision	Rationale
7.2.2; 7.2.3; 7.3.2; 7.3.3	Corrected last bullet by adding “or EMG” to the devices for muscle localization techniques Clarified that MAS-B and MTS for finger flexors will be analyzed for the subgroup of patients with wrist identified as the principal muscle group	Correction Clarification
7.3.1	The original multiple testing procedure (Fisher’s Protected Testing procedure) was changed to a gatekeeping procedure Pairwise comparison for high dose versus low dose was removed Overall test for among-group comparison was removed	To control type I error rate To incorporate US FDA recommendation Gatekeeping procedure for the 2 pairwise comparisons is sufficient to control type I error rate
7.3.1; 11	CGI by Physician was removed for non-US FDA primary analyses Removed Saville citation and reference	Clarification No longer applicable due to the multiple testing procedure change
7.3.2	CGI by Physician was added for non-US FDA analyses as a secondary measure	Clarification
7.4	Removed subgroup efficacy analyses by type of anesthesia	The distribution and number of patients in each type of anesthesia will not produce meaningful efficacy results.
Protocol summary; 7.5	Revised sample size calculation to base the calculation on 2-sample t-test	Since the overall test for among group comparison was removed
7.7	Added separate sections (7.7.1 and 7.7.2) to specify the primary and secondary efficacy analyses for FDA and added a table for efficacy claim	Clarification and to incorporate US FDA recommendation
8.3.1; 12.1.4	Amended sentence to remove time frame for blood sample collection	Clarification
Table 1; 8.3.1; 8.3.3	Removed passive range of motion bullet to indicate that assessment of passive range of motion can be performed as part of the MTS using the angle of slow stretch (R2)	Clarification
8.3.3	Added bullets for review of screening laboratory results and accessing IVRS/IWRS to randomize patients Added “in kilograms” to weight measurement	Clarification of day 1 procedures Clarification

Section(s)	Revision	Rationale
8.3.4	[REDACTED]	Clarification of visit 8 procedures
8.3.5	Added [REDACTED] use of IVRS/IWRS	Clarification of visit 8 procedures
9.3	Updated serious adverse event reporting procedure	Per new Allergan protocol template
12.1.1	Amended second sentence regarding weight measurements	Clarification on requirements for weight measurements and that weight must be measured in kilograms
12.1.2	Added “temporal, rectal” to body temperature	As per common practices
12.1.10	Deleted “physician”	To clarify that other qualified site personnel can perform the MAS-B
	Revised MAS-B description to say “study-specified” instead of “non-study-specified” velocity	To clarify that we do instruct the sites on a specific velocity
12.1.11	Merged sections 12.1.11 and 12.1.12 to indicate that assessment of passive range of motion can be performed as part of the MTS using slow stretch (V1)	Clarification
12.1.12, 12.1.15	Amended “investigator” to “physician investigator”	Clarification

12.6 Protocol Amendment 3 Summary (October 2015)

Title: BOTOX® Treatment in Pediatric Upper Limb Spasticity: Double-blind Study

Protocol 191622-101, Amendment 3

Date of Amendment: October 2015

Amendment Summary

This summary includes changes made to Protocol 191622-101 Amendment 2 (January 2014). This protocol was amended to decrease the sample size and to incorporate changes in statistical procedures.

Following is a summary of content-oriented changes that were made to each section of the protocol, and a brief rationale for these changes. Minor editorial and document formatting revisions have not been summarized.

Section(s)	Revision	Rationale
Title page	Updated Allergan Medical Safety Physician and Allergan signatory information	Change in staff
Protocol Summary, 4.1 (Number of Patients)	Estimated number of patients to complete study was decreased from 351 to 213	Recalculated sample size based on adjusted treatment differences from upper limb studies
Protocol Summary; 7.5 (Sample Size Calculation)	Number of patients and sample size calculations were revised	Recalculated sample size based on adjusted treatment differences from upper limb studies
7.2 (Collection and Derivation of Primary and Secondary Efficacy Assessments)	Added sensitivity analyses (MMRM and summary of percentage of missing data for the primary variables)	To supplement primary analysis using observed data, not imputed data for primary analysis
7.3 (Hypothesis and Methods of Analysis)	Statistical analysis method (ANOVA) was changed to ANCOVA (added study center and previous botulinum toxin exposure as factors) and changed baseline MAS-B to continuous variable	To obtain more consistent results and increase model power
7.7 (Additional Analysis/Inference for US FDA)	Multiple testing procedure (gatekeeping procedure) was changed to Hochberg procedure for the co-primary analysis for US FDA	To control type I error rate

12.7 Protocol Amendment 3 Summary (January 2016)

Title: BOTOX® Treatment in Pediatric Upper Limb Spasticity: Double-blind Study

Protocol 191622-101, Amendment 3

Date of Amendment: January 2016

Amendment Summary

This summary includes changes made to Protocol 191622-101 Amendment 3 (October 2015). This protocol was amended to incorporate FDA recommendations.

Following is a summary of content-oriented changes that were made to each section of the protocol and a brief rationale for these changes. Minor editorial and document formatting revisions have not been summarized.

Section(s)	Revision	Rationale
Title page	Updated Allergan Medical Safety Physician and Allergan signatory information	Personnel changes
Protocol Summary, 7.1 (Analysis Populations), 7.3 (Hypothesis and Methods of Analysis)	The intent-to-treat (ITT) population was replaced with the mITT population, which is defined as all randomized patients with a valid MAS-B baseline score of the principle muscle group and at least one post-baseline measurement at weeks 2, 4, or 6 for the MAS-B of the principle muscle group and the CGI by Physician.	Revised based on FDA recommendation
Protocol Summary, 7.5 (Sample Size Calculation)	The sample size assumptions and power calculations tables (Protocol Summary and Table 4) are now in agreement	Correction
7.2 (Collection and Derivation of Primary and Secondary Efficacy Assessments), 7.3 (Hypothesis and Methods of Analysis), 7.7 (Additional Analysis/Inference for US FDA)	The primary MAS-B analysis and FDA co-primary MAS-B and CGI analyses were changed to use the MI method for missing values instead of observed cases; sensitivity analyses using last observation carried forward (LOCF) were removed.	Based on FDA feedback on handling missing data for the primary analysis

Section(s)	Revision	Rationale
7.3 (Hypothesis and Methods of Analysis)	Text describing sensitivity analyses was edited to spell out the covariate and factors in the MMRM model; factors for logistic regression were updated to match the primary analysis model; analyses of co-primary endpoints for US FDA were moved to Section 7.7	For clarification
7.7 (Additional Analysis/Inference for US FDA)	Sensitivity analyses using MMRM and ANCOVA to support the co-primary analysis for US FDA are now described in this section	For clarification

1.1 Primary Study Objectives and Design

The primary objective of the study is to evaluate the safety and efficacy of a single treatment of 2 doses (3 U/kg and 6 U/kg) of BOTOX with standardized occupational therapy (OT) in pediatric patients with upper limb spasticity.

This is a multicenter, randomized, double-blind, placebo-controlled, parallel-group, 12-week study evaluating 2 doses of BOTOX, 6 U/kg, 3 U/kg, and placebo with standardized OT for the treatment of monoplegic, hemiplegic, or triplegic children with upper limb spasticity due to cerebral palsy or stroke.

A centralized randomization scheme stratified by age group, principal muscle group, and baseline modified Ashworth Scale – Bohannon (MAS-B) will be used. Patients will be randomized to 1 of 3 treatment groups in a 1:1:1 ratio within each combination of strata. The stratification categories are as follows:

1. Age (≤ 6 years and > 6 years)
2. Designated principal muscle group (elbow flexors and wrist flexors)
3. Baseline (day 1) MAS-B score of the principal muscle group (MAS-B = 2 and MAS-B > 2)

There will be 1 treatment cycle in the study. The maximum study duration per patient will be approximately 16 weeks (including up to 4 weeks in the screening period). Patients will complete 8 study visits as follows: screening (week -4 to week -2), initiation of standardized OT (week -2), randomization and treatment visit (day 1), and post-injection follow-up visits at weeks 2, 4, 6, 8, and 12. All patients will receive weekly OT sessions from week 2 through week 11.

Patients who successfully complete this study without major protocol deviations (eg, non-compliance to protocol required procedures) will be given the option of enrolling in open-label extension Study 191622-105 if they meet eligibility criteria.

Sample size calculation and power consideration are presented in Section 7.5 of the study protocol.

1.2 Secondary and Other Objectives

There are no secondary or other objectives for this study.

2 Analysis Populations and Data Conventions

2.1 Analysis Populations

Two populations will be used in the statistical analysis: safety population and modified intent-to-treat (mITT) population. If any patient is mis-stratified by the site at randomization on day 1, this patient's data will be included in the stratum based on the patients' actual age and baseline MAS-B for the age and baseline MAS-B group, and the actual injected muscle group for the principal muscle group instead of the interactive voice response system (IVRS) stratum for analysis.

The safety population will include all treated patients. All safety analyses will be based on the actual treatment received by each patient in this population.

The mITT population will include all randomized patients with a valid MAS-B baseline score of the principal muscle group and at least one post-baseline measurement at weeks 2, 4, or 6 for the MAS-B of the principal muscle group and the Clinical Global Impression of Overall Change (CGI) by Physician. Here weeks 2, 4, and 6 refer to the analysis visits defined in Section 2.2. The mITT population will be analyzed according to randomization assignment, regardless of treatment actually received. Efficacy data, demographics, and other baseline characteristics will be analyzed using the mITT population.

2.2 Treatment Visits

All days are referenced to day 1. Day 1 is the randomization/treatment day. In the cases where randomization and treatment happened on different days, the day of treatment will be used as day 1. Visits according to the windows below will be determined for each variable analyzed unless noted otherwise in the following sections. If there are values from multiple visits in a given window, the value collected from the visit closest to the target day will be used to represent the window. If 2 visits with values fall within the same window and are equidistant from the target day, the value from the first of the 2 visits chronologically will be used to represent the window. For clinical laboratory variables, the last non-missing observation for that visit window

will be used. This rule will be applied separately for each variable for non-missing data only. (The exception is because re-runs of laboratory variables may only involve one or a few variables and would thus include missing data for many variables).

Visit	Target Day of the Visit	Visit Window (Day*)
Screening	-28	\leq Day -1
Day 1 (Randomization/Treatment)	1	Day 1
Week 2	15	Day 2 to Day 22
Week 4	29	Day 23 to Day 36
Week 6	43	Day 37 to Day 50
Week 8	57	Day 51 to Day 71
Week 12	85	\geq Day 72

* All days are referenced to day 1. For post-treatment visits, study day = visit date – day 1 date+1 while for pre-treatment visits, study day = visit date - day 1 date.

The visit windows will be used for by-visit analyses in both modified intent-to-treat (mITT) and safety population analyses.

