12.1.4 Hematology and Serum Chemistry

During screening, patients will need to have a blood sample for laboratory evaluations collected after informed consent is signed. Another blood sample will be collected at the study exit visit. Blood specimens will be collected using standard laboratory instructions and procedures provided by the central laboratory. Fasting blood samples should be collected unless the patient is not able to fast for approximately 8 hours. Patients who are willing to fast and did not come to the screening visit in a fasting state may return prior to the day 1

BOTOX® (Botulinum Toxin Type A) Purified Neurotoxin Complex

visit for blood sample collection as long as the laboratory results can be received and reviewed at or before the day 1 visit. The blood specimens will be analyzed for the following:

Hematology	hemoglobin	hematocrit	red blood cells
	white blood cells	neutrophils	bands
	lymphocytes	monocytes	basophils
	eosinophils	platelets	
Electrolytes	sodium	potassium	bicarbonate
	chloride	phosphorus	calcium
Chemistry	glucose	creatinine	urea nitrogen
	total bilirubin	alkaline phosphatase (total plus bone and liver fractions)	aspartate aminotransferase (serum glutamic oxaloacetic transaminase)
	alanine aminotransferase (serum glutamic pyruvic transaminase)	albumin	
Other	HbA1c	25 hydroxyl vitamin D	Parathyroid hormone if alkaline phosphatase bone fraction is abnormal

Reference ranges for alkaline phosphatase and glucose are shown in Table 5.

Table 5**Reference Ranges for Alkaline Phosphatase and Glucose**

Parameter	Age (Years)	Range
Alkaline phosphatase		
Female	1 to 3	125 to 320 U/L
	4 to 6	150 to 370 U/L
	7 to 9	150 to 440 U/L
	10 to 11	150 to 530 U/L
	12 to 13	110 to 525 U/L
	14 to 15	55 to 305 U/L
	16 to 19	40 to 120 U/L
Male	1 to 3	125 to 320 U/L
	4 to 6	150 to 370 U/L
	7 to 9	150 to 440 U/L
	10 to 11	150 to 470 U/L
	12 to 13	160 to 500 U/L
	14 to 15	130 to 530 U/L
	16 to 19	60 to 270 U/L
Bone-specific alkaline phosphatase (ostase)		
Female	1 to 6	0 to 189 U/L
	7 to 9	0 to 246 U/L
	10 to 13	0 to 340 U/L
	14 to 15	0 to 91 U/L
	≥ 16	0 to 55 U/L
Male	1 to 6	0 to 208 U/L
	7 to 9	0 to 264 U/L
	10 to 15	0 to 340 U/L
	16 to 19	0 to 165 U/L
Glucose	All ages	70 to 100 mg/dL, 3.9 to 5.6 mmol/L

Note: Reference ranges were received from Covance Laboratory as of 16 January 2012.

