- Data from unscheduled visits or re-test visits will be treated the same way as scheduled visits, ie, the dates of such visits will be used in the categorization of visit window. The algorithm handling multiple visits within a visit window will also be applied to unscheduled visits and re-test visits.
- For the primary and secondary efficacy analyses where study center is a factor in the analysis model, centers that recruited only a few patients will be pooled together. The following algorithm for pooling study centers will be used:
 - A. Pooling of study centers will by country.
 - B. Within each country, the following will be conducted:

1. Study centers will be ranked in descending order of the total number of patients enrolled.
2. Any center with at least 12 patients will stand on its own.
3. The first center with fewer than 12 patients will be combined with the next smallest center until the total number in the pooled center reaches or exceeds 12 patients.
4. The algorithm of combining centers will continue down the list as described above.
5. If the last pooled center still has less than 12 patients, the last pooled center will be combined with the previous pooled center.

C. If there are less than 12 subjects enrolled in a country, the country will be pooled to the smallest center in the same region (alphabetical order if there is a tie). The regions include Asian Pacific, Europe, and North America. For example, if Canada enrolled less than 12 patients, Canada will be pooled with a smallest center in the United States.

- The mean change from baseline for a given treatment group will be calculated by taking the sum of all individual changes from baseline divided by the number of patients with observations in that treatment group. As a consequence, patients without the particular follow-up data will not be taken into account, except if there is a missing value replacement method used.
- [REDACTED]

3 Disposition and Exit Status

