6.4 Clinical Laboratory Evaluations

Hematology and non-fasting clinical chemistry assays will be obtained at screening and exit as specified below.

Hematology	hemoglobin	hematocrit	red blood cells
	white blood cells	neutrophils	bands
	lymphocytes	monocytes	basophils
	eosinophils	platelets	
Electrolytes	sodium	potassium	bicarbonate
	chloride	phosphorus	calcium
Chemistry	glucose	creatinine	urea nitrogen
	total bilirubin	alkaline phosphatase (total plus bone and liver fractions)	aspartate aminotransferase (serum glutamic oxalacetic transaminase)
	alanine aminotransferase (serum glutamic pyruvic transaminase)	albumin	
Other	hemoglobin A1c	25 hydroxyl vitamin D	Parathyroid hormone if alkaline phosphatase bone fraction is abnormal

These values at each visit and the change from baseline will be summarized by the treatment group by visits using descriptive statistics. All laboratory values will be listed. Laboratory values at each visit will also be categorized as low, normal, and high according to the respective reference normal ranges.

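### The by-visit laboratory tables keep the last value in each window, so a normal repeat replaces an abnormal exit result, and early exit samples are not tabulated with the other exit samples

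*SAP*

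**What the plan says.** Blood is drawn for safety tests at screening, and then: "Another blood sample will be collected at the study exit visit" (Protocol 12.1.4). SAP 6.4 names the same two time points, so the plan has one scheduled post-treatment laboratory result per patient.

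SAP 2.2 has two rules for windows that hold more than one result. For most variables, "the value collected from the visit closest to the target day will be used to represent the window". For laboratory data the rule differs: "For clinical laboratory variables, the last non-missing observation for that visit window" is the one used, variable by variable. The reason offered is partial repeats: "The exception is because re-runs of laboratory variables may only involve one or a few variables".

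SAP 2.3 brings repeats into this scheme: "Data from unscheduled visits or re-test visits will be treated the same way as scheduled visits", and "The algorithm handling multiple visits within a visit window will also be applied to unscheduled visits and re-test visits". SAP 2.2 adds that "The visit windows will be used for by-visit analyses in both modified intent-to-treat (mITT) and safety population analyses". Its last window, Week 12, starts at Day 72 and has no end. None of the windows is called exit.

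SAP 6.4 then summarises values and changes by visit, and "Laboratory values at each visit will also be categorized as low, normal, and high according to the respective reference normal ranges". It also promises a listing of every laboratory value. Protocol 7.3.4 mentions a shift table, again by visit, and leaves a summary of potentially clinically significant values optional, without criteria. SAP 6.4 takes up neither. Neither document plans a table by worst post-treatment value or by any post-treatment abnormality.

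**The concern.** With a single scheduled post-treatment sample, the laboratory safety tables depend on which result stands for that sample. Under these rules it is the exit result if nobody repeats the test, and the repeat if somebody does. The low/normal/high count in an arm therefore depends partly on repeat testing, which the protocol does not standardise. If repeats are mostly prompted by abnormal results, the table will show fewer abnormalities than were observed after treatment.

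The second issue is where exit samples are counted. Protocol 8.7 requires the Week 12 procedures, blood sampling included, when a patient leaves early. With windows set by study day only, that sample is tabulated at an earlier week and not beside the exit samples of completers. Patients who leave early may include some who left for safety reasons, so one exit summary covering everyone would be more informative.

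**Working it through.** The plan states no figure on this point, so there is nothing to reproduce. The check is to apply the rules to short sequences of results and see what the tables would show.

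**Inputs.** Windows from SAP 2.2: Week 2 = Day 2 to 22, Week 4 = Day 23 to 36, Week 6 = Day 37 to 50, Week 8 = Day 51 to 71, Week 12 = Day 72 onward (target Day 85). Laboratory rule: last non-missing value in the window. Re-tests are windowed by date (SAP 2.3). The closest-to-target rule used for other variables is shown for comparison.

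| Exit result, then repeat | Last value (laboratory rule) | Closest to target |
|---|---|---|
| Day 85 high, Day 92 normal | Week 12 normal | Week 12 high |
| Day 85 high, Day 120 normal | Week 12 normal | Week 12 high |
| Day 85 normal, Day 92 high | Week 12 high | Week 12 normal |
| Day 78 high, Day 85 normal | Week 12 normal | Week 12 normal |
| Day 40 high, Day 47 normal | Week 6 normal | Week 6 high |
| Day 48 high, Day 55 normal | Week 6 high, Week 8 normal | the same |
| Day 70 high, Day 77 normal | Week 8 high, Week 12 normal | the same |

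Four things follow.

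1. For an exit on Day 72 or later, any later normal repeat in the study data replaces the abnormal value, because the window never closes.
2. The rule works both ways: in the third row a normal exit value becomes high.
3. When an exit before Day 72 is followed by a repeat in a later window, both results are tabulated.
4. Switching laboratory data to the closest-to-target rule would not be a full remedy, as the fourth row shows.

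**Size of the replacement effect.** Let n be the patients in an arm, p the proportion abnormal at exit on a given test, and f the share of those whose abnormal value is replaced by a normal repeat. Leaving aside normal values that become abnormal on repeat, the number tabulated as abnormal is n × p × (1 − f). The documents give neither p nor f. The table below only shows how the formula behaves, with n = 71 (planned completers per group) and p and f assumed:

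| p | n × p (f = 0) | f = 25% | f = 50% | f = 80% |
|---|---|---|---|---|
| 3% | 2.1 | 1.6 | 1.1 | 0.4 |
| 5% | 3.6 | 2.7 | 1.8 | 0.7 |
| 10% | 7.1 | 5.3 | 3.6 | 1.4 |

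If repeats are rare, f is near zero and nothing is lost.

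**Arms.** With the same f in two arms, the tabulated difference is n × (1 − f) × (p₁ − p₂), and the ratio stays p₁/p₂. The absolute difference shrinks and the relative comparison is unchanged.

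**Early exits.** Protocol 7.5 plans 224 enrolled and at least 213 completing: 224 − 213 = 11, and 11/224 = 4.9%. This is an upper figure under the plan's allowance, because anyone leaving on Day 72 or later still falls in Week 12.

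**The case against.** The best defence has five parts.

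- **The rule has a stated purpose.** When a repeat covers only one or a few analytes, or replaces an unreportable one, the last non-missing value is sensible. This stands for missing or invalid results. It does not explain why a valid exit result should give way to a later one; working variable by variable on non-missing data already handles partial repeats.
- **Repeats after exit are not planned.** Protocol 8.7 treats the patient's last visit as the exit visit, and children who continue go straight into the extension study (Protocol 8.3.5), where a later repeat may be recorded instead. This stands: how often the replacement would occur is unknown. However, Protocol 8.5 allows unscheduled visits for safety concerns with case report forms completed, and SAP 2.3 plans for re-tests, so the situation is foreseen.
- **Nothing is hidden.** Both results appear in the listing, and Protocol 9.1.1 allows an abnormal laboratory finding to be an adverse event, so it may reach the adverse event tables. This stands. Listings give no counts per arm, though, and adverse event reporting rests on the investigator's judgement.
- **An exit row may be intended.** SAP 2.2 allows later sections to depart from its windows, and SAP 6.4 names exit as a time point. That reading is possible, but SAP 6.4 does not state it, whereas SAP 6.5 explicitly provides change to the exit visit for vital signs.
- **The tables are descriptive and the rule is the same in every arm.** Both are true, and they limit the importance of the point.

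**Conclusion.** The point holds as a gap in the safety summary that should be closed. An abnormal exit result on Day 72 or later that is normal on repeat, with the repeat in this study's data, is tabulated as normal, and no other planned laboratory table is sure to count it. The extent depends on how often exit samples are repeated and why, and the documents give no basis for an estimate. Separately, exit samples taken before Day 72, from at most about 11 of 224 patients, are split from the rest.

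A reader might infer more, and the documents do not support it:

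- **That abnormal results are erased.** They leave the by-visit tables only.
- **That the rule always turns abnormal into normal.** It is neutral. The downward effect needs repeats to follow abnormal results, which is plausible but stated nowhere.
- **That a given percentage of abnormalities is lost.** Any such figure comes from assumed repeat and normalisation rates.
- **That one arm benefits.** The same rule applies to all arms, and equal replacement rates preserve the ratio between them.
- **That early leavers drop out of the laboratory analysis.** Their samples are tabulated, under an earlier week.

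**What to change.** Amend SAP 6.4, with a cross-reference in SAP 2.2:

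1. Add a table per arm that classifies each patient by worst post-treatment value, taking the lowest and the highest result over all scheduled, unscheduled and re-test samples, regardless of window, against the reference range.
2. Summarise laboratory values and changes from baseline at one exit time point, using the scheduled exit sample whatever its study day. Use a re-test only if the scheduled result is missing or invalid.

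The baseline definition in SAP 2.3 can stay as it is. The cost is a few sentences and one more table from data already collected; no procedure or efficacy analysis changes. The downside is that the worst-value table will show slightly more abnormalities in every arm, which a footnote on its definition can explain.
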